**C. Additional principles for medical research combined with medical care**

1. The physician may combine medical research with medical care, only to the extent that the research is justified by its potential prophylactic, diagnostic or therapeutic value. When medical research is combined with medical care, additional standards apply to protect the patients who are research subjects.
2. The benefits, risks, burdens and effectiveness of a new method should be tested against those of the best current prophylactic, diagnostic, and therapeutic methods. This does not exclude the use of placebo, or no treatment, in studies where no proven prophylactic, diagnostic or therapeutic method exists.

To clarify further the WMA position on the use of placebo-controlled trials, the WMA Council issued, during October 2001, a note of clarification on article 29.

1. At the conclusion of the study, every patient entered into the study should be assured of access to the best proven prophylactic, diagnostic and therapeutic methods identified by the study.
2. The physician should fully inform the patient which aspects of the care are related to the research. The refusal of a patient to participate in a study must never interfere with the patient–physician relationship.
3. In the treatment of a patient, where proven prophylactic, diagnostic and therapeutic methods do not exist or have been ineffective, the physician, with informed consent from the patient, must be free to use unproven or new prophylactic, diagnostic and therapeutic measures, if in the physician's judgement it offers hope of saving life, re-establishing health or alleviating suffering. Where possible, these measures should be made the object of research, designed to evaluate their safety and efficacy. In all cases, new information should be recorded and, where appropriate, published. The other relevant guidelines of this Declaration should be followed.

**D. Note of clarification on paragraph 29 of the WMA Declaration of Helsinki**

The WMA is concerned that paragraph 29 of the revised Declaration of Helsinki (October 2000) has led to diverse interpretations and possible confusion. It hereby reaffirms its position that extreme care must be taken in making use of a placebo-controlled trial and that in general this methodology should only be used in the absence of existing proven therapy. However, a placebo-controlled trial may be ethically acceptable, even if proven therapy is available, under the following circumstances:

1. Where for compelling and scientifically sound methodological reasons it is necessary to determine the efficacy or safety of a prophylactic, diagnostic or therapeutic method; or
2. Where a prophylactic, diagnostic or therapeutic method is being investigated for a minor condition and the patients who receive placebo will not be subject to any additional risk of serious or irreversible harm.

All other provisions of the Declaration of Helsinki must be adhered to, especially the need for appropriate ethical and scientific review.

Note of clarification on paragraph 29 of the WMA Declaration of Helsinki. The WMA is concerned that paragraph 29 of the revised Declaration of Helsinki (October 2000) has led to diverse interpretations and possible confusion. It hereby reaffirms its position that extreme care must be taken in making use of a placebo-controlled trial and that in general this methodology should only be used in the absence of existing proven therapy. However, a placebo-controlled trial may be ethically acceptable, even if proven therapy is available, under the following circumstances:

1. Where for compelling and scientifically sound methodological reasons it is necessary to determine the efficacy or safety of a prophylactic, diagnostic or therapeutic method; or
2. Where a prophylactic, diagnostic or therapeutic method is being investigated for a minor condition and the patients who receive placebo will not be subject to any additional risk of serious or irreversible harm.

All other provisions of the Declaration of Helsinki must be adhered to, especially the need for appropriate ethical and scientific review.

18. Deviations from Protocol-Stated Analyses 24

19. References..... 25

20. Tables 25

21. Listings 26

22. Figures 27

Protocol RGN-NK-301/15-110-0006, SAP Version 1.0

List of Abbreviations

Abbreviation	Definition
AE	Adverse Event
ANCOVA	Analysis of Covariance
ATC	Anatomical Therapeutic Chemical
BCVA	Best Corrected Visual Acuity
CI	Confidence Interval
CRF	Case Report Form
CS	Clinically Significant
eCRF	Electronic Case Report Form
ETDRS	Early Treatment of Diabetic Retinopathy Study
HIPAA	Health Information Portability and Accountability Act
ICH	International Conference on Harmonization
IOP	Intraocular Pressure
ITT	Intent-to-Treat
LOCF	Last Observation Carried Forward
logMAR	Logarithm of the Minimum Angle of Resolution
MedDRA	Medical Dictionary for Regulatory Activities
MI	Multiple Imputation
NCS	Not clinically significant
NK	Neurotrophic Keratopathy
PDF	Portable Document Format
PP	Per Protocol
PT	Preferred Term
RTF	Rich Text Format
SAE	Serious Adverse Event
SAP	Statistical Analysis Plan
SD	Standard Deviation
SDC	Statistics and Data Corporation, Incorporated
SOC	System Organ Class
TEAE	Treatment-Emergent Adverse Event
TFBUT	Tear Film Break-up Time
VA	Visual Acuity
WHODrug	World Health Organization Drug Dictionary

Protocol RGN-NK-301/15-110-0006, SAP Version 1.0

1. Introduction

The purpose of this statistical analysis plan (SAP) is to describe the planned analyses and reporting for protocol RGN-NK-301/15-110-0006, version 5.0 dated 04May2017.

This SAP is being written with due consideration of the recommendations outlined in the most recent International Conference on Harmonization (ICH) E9 Guideline entitled Guidance for Industry: Statistical Principles for Clinical Trials and the most recent ICH E3 Guideline, entitled Guidance for Industry: Structure and Content of Clinical Study Reports.

This SAP describes the data that will be analyzed and the subject characteristics, efficacy, and safety assessments that will be evaluated. This SAP provides details of the specific statistical methods that will be used. The statistical analysis methods presented in this document will supersede the statistical analysis methods described in the clinical protocol. If additional analyses are required to supplement the planned analyses described in this SAP, they may be completed and will be identified in the CSR.

2. Study Objectives

The objective of this study is to compare the safety and efficacy of RGN-259 Ophthalmic Solution to placebo for the treatment of neurotrophic keratopathy (NK).

3. Study Variables

3.1 Primary Variables

The primary efficacy variable is the following:

- [Redacted]

3.2 Secondary Variables

The secondary efficacy variables include the following:

- [Redacted]
- [Redacted]
- [Redacted]
- [Redacted]
- [Redacted]

Protocol RGN-NK-301/15-110-0006, SAP Version 1.0

3.3 Safety Variables

The safety variables include the following:

- VA assessed by Early Treatment of Diabetic Retinopathy Study (ETDRS) scale;
- Slit-Lamp Biomicroscopy;
- Cochet-Bonnet;
- Adverse Event (AE) Query;
- Dilated Fundoscopy;
- Intraocular Pressure (IOP).

3.4 Statistical Hypotheses

H₀: There is no difference between study eyes treated with RGN-259 and study eyes treated with placebo, RGN-259 – placebo, in the percentage of study eyes achieving complete healing of epithelial defect at Day 29 (Visit 5).

H_A: There is a difference between study eyes treated with RGN-259 and study eyes treated with placebo, RGN-259 – placebo, in the percentage of study eyes achieving complete healing of epithelial defect at Day 29 (Visit 5).

[REDACTED]

4. Study Design and Procedures

4.1 General Study Design

This is a Phase 3, multicenter, randomized, double-masked, placebo controlled safety and efficacy study. It consists of two treatment arms, a 0.1% concentration of RGN-259 ophthalmic solution and placebo ophthalmic solution, [REDACTED]. There are seven scheduled visits over approximately 6 weeks (43 days), with approximately 100 subjects being screened [REDACTED]. [REDACTED]. Visit 1 (Day 1) is the screening visit, as well as the baseline visit for subjects who are eligible for the study. Eligible subjects will be randomized to receive one of the two study treatments. Randomized subjects will then begin using study drug in the affected eye(s) 5 times per day for 28 days.

[figure not shown]
Study visits will be referred to in all tables and listings as the expected study day corresponding to the visit to enable reviewers to understand the assessment timing without referring to the protocol visit schedule. The following table shows the scheduled study visits, their planned study day (Day 1 corresponds to the day of randomization), and the acceptable visit window for each study visit:

Protocol RGN-NK-301/15-110-0006, SAP Version 1.0

Scheduled Visit	Planned Study Day	Visit Window
Visit 1	Day 1	n/a
Visit 2	Day 8	± 2 Days
Visit 3	Day 15	± 2 Days
Visit 4	Day 22	± 2 Days
Visit 5	Day 29	± 2 Days
Visit 6	Day 36	± 3 Days
Visit 7	Day 43	± 3 Days

4.2 Schedule of Visits and Assessments

The schedule of visits and assessments is provided below.

4.3 Early Termination of the Study

Due to the rarity of the disease and the roughly 5 year enrollment period at multiple sites the Sponsor has decided to end this phase 3 trial based on the lack of enrollment. Even with the extended enrollment period, only 18 subjects were enrolled and subsequently completed the study. Analyses will be

Protocol RGN-NK-301/15-110-0006, SAP Version 1.0

conducted as originally intended; however, the study is no longer powered to detect statistical differences. See the revised power calculations in section 6.1 of this SAP.

As with other studies of rare diseases this study will focus on clinically meaningful difference. Clinically meaningful results will be assessed by the Sponsor’s medical and/or regulatory teams.

5. Study Treatments

The study treatments are 0.1% RGN-259 Ophthalmic Solution and Placebo Ophthalmic Solution (Vehicle).

5.1 Method of Assigning Subjects to Treatment Groups

At Visit 1, subjects who provide written informed consent will be assigned a unique 5-digit screening number, which includes the 2-digit site number plus a unique 3-digit screening number beginning with 001 (e.g., 11001, 11002, 11003, etc.). Screening numbers must be assigned in ascending consecutive order.

If all inclusion and exclusion criteria are met at Visits 1, each qualifying subject will then be assigned a 4-digit randomization number at the end of Visit 1. All randomization numbers will be assigned in strict numerical sequence and no numbers will be skipped or omitted. Assignment of qualified subjects to a treatment group will be accomplished by using a randomization code generated by an independent biostatistician. Investigators and study staff who will conduct the assignment procedure will be masked to the randomization code.

5.2 Masking and Unmasking

This is a double-masked study. Subjects, Investigators and site staff, sponsor and Ora/Statistics & Data Corporation (SDC) study staff are masked to the treatment group assignments for the duration of the study. The randomization schedule was created by an unmasked statistician who is not otherwise involved in the conduct of the study.

Under normal circumstances, the mask should not be broken. When medically necessary, the investigator may need to determine what treatment arm has been assigned to a subject. When possible (i.e., in non-emergent situations), Ora and/or the study sponsor should be notified before unmasking study drug.

6. Sample Size and Power Considerations

[REDACTED]

Protocol RGN-NK-301/15-110-0006, SAP Version 1.0

[REDACTED]

6.1 Revised Power Calculations

Due to the rarity of the disease and the Sponsor's early termination of the study the proposed sample size of 42 will not be attained. [REDACTED]

[REDACTED]

7. Data Preparation

All reported study data will be recorded on the electronic case report forms (eCRFs) supplied by SDC using iMedNet™. Only the Principal Investigator and authorized study staff according to the Delegation of Responsibilities log are entitled to make entries in the eCRF.

After data are entered into the clinical study database, electronic edit checks and data review will be performed. All data validation specifications and procedures are detailed in the Data Validation Manual as a separate document. When the database has been declared to be complete and accurate, the database will be locked. Any changes to the database after data have been locked can only be made with the approval of the Sponsor and Ora in consultation with SDC.

All analyses outlined in this document will be carried out after the following have occurred:

- All data management requirements are met according to SDC standard operating procedures, including data entry, performance of edit and validation checks, documentation and resolution of data queries, and database lock with written authorization provided by appropriate SDC and Sponsor personnel;
- Protocol deviations have been identified and status defined (major/minor deviations);
- Analysis populations have been determined; and
- Randomized treatment codes have been unmasked.

Protocol RGN-NK-301/15-110-0006, SAP Version 1.0

8. Analysis Populations

8.1

[REDACTED]

8.2

[REDACTED]

8.3 Safety

The safety population includes all randomized subjects who have received at least one dose of the investigational medicinal product. The safety population will be analyzed for all safety assessments according to the treatment actually received.

The statistical analysis of safety data will be performed for the safety population. The analysis of baseline and efficacy data will be performed for the ITT population. The primary efficacy analysis will also be performed on the PP population as sensitivity analyses.

9. General Statistical Considerations

9.1 Unit of Analysis

The unit of analysis in this study will be the study eye for all efficacy summaries and any treated eye for ocular safety summaries. In general, NK is unilateral. If a patient presents with bilateral epithelial defects that both meet the entry criteria, the study eye will be defined as the affected eye with the largest affected area, and the other eye will be considered a qualified fellow eye. If both affected eyes have the same affected area, the right eye will be the study eye and the left eye will be considered a qualified fellow eye.

Ocular AEs will be summarized for all eyes and for any treated eye (if at least one subject has bilateral NK in which both eyes are treated), and ocular safety assessments will be analyzed by study eye and both treated eyes (again, if at least one subject has bilateral NK in which both eyes are treated), where the worst safety outcome over both eyes is summarized. Medical history and non-ocular AEs and safety assessments will be presented at the subject level.

9.2 Missing or Inconclusive Data Handling

[REDACTED]

Protocol RGN-NK-301/15-110-0006, SAP Version 1.0

[REDACTED]

9.3 Definition of Baseline

Baseline measures are defined as the last measure prior to the initiation of study treatment, usually at Visit 1 (Day 1).

9.4 Data Analysis Conventions

All data analysis will be performed by SDC after the study is completed and the database has been locked and released for unmasking. Statistical programming and analyses will be performed using [REDACTED]. Output will be provided in rich text format (RTF) format for tables and portable document file (PDF) format for tables, listings, and figures using landscape orientation. All study data will be listed by subject, treatment, visit (as applicable), and time point (as applicable) based on all randomized subjects unless otherwise specified.

[REDACTED]

[REDACTED]

[REDACTED]

9.5 Adjustments for Multiplicity

[REDACTED]

Protocol RGN-NK-301/15-110-0006, SAP Version 1.0

10. Disposition of Subjects

Subject disposition will be presented in terms of the numbers and percentages [REDACTED]

[REDACTED]

[REDACTED]

[REDACTED]

[REDACTED]

[REDACTED]

[REDACTED]

[REDACTED]

[REDACTED]

[REDACTED]

[REDACTED]

[REDACTED]

[REDACTED]

[REDACTED]

[REDACTED]

[REDACTED]

[REDACTED]

[REDACTED]

[REDACTED]

[REDACTED]

[REDACTED]

[REDACTED]

[REDACTED]

[REDACTED]

[REDACTED]

11. Demographic and Pretreatment Variables

11.1 Demographic Variables

The demographic variables collected in this study include age, sex, race, ethnicity, and iris color. Subjects who record more than one race will be grouped into a single category denoted as multi-racial. Demographic variables will be summarized for the ITT population and Safety populations, separately.

Age (years) will be summarized, overall and by treatment, using continuous descriptive statistics. Age will also be categorized as follows: [REDACTED]

[REDACTED]

The number and percentage of subjects will be presented, overall and by treatment, for age category, sex, race, ethnicity and iris color (by study eye).

No statistical inference testing will be performed for the demographic variables. A subject listing that includes all demographic variables will be provided.

Protocol RGN-NK-301/15-110-0006, SAP Version 1.0

11.2 Pretreatment Variables and Baseline Disease Characteristics

[REDACTED]

[REDACTED]

[REDACTED]

[REDACTED]

12. Medical History, Prior and Concomitant Medications

12.1 Medical History

Medical history will be coded using the Medical Dictionary for Regulatory Activities (MedDRA) Version 22.0.

Non-ocular medical history will be summarized using discrete summary statistics and presented by treatment group at the subject and event level by System Organ Class (SOC) and Preferred Term (PT) using the Safety population. Ocular medical history will be similarly summarized at the subject level. If a subject reports the same PT multiple times within the same SOC, that PT will only be reported once within that SOC. As with the PT, if a subject reports multiple conditions within the same SOC, that SOC will only be reported once.

Listings of medical history will be generated separately for ocular and non-ocular data.

12.2 Concomitant Medications

Prior and concomitant medications will be coded using the World Health Organization Drug Dictionary (WHODrug Global, B3, March 2019) and summarized to the therapeutic drug class (Anatomical Therapeutic Chemical (ATC) 4 classification) and preferred name (drug name).

Concomitant medications are defined as those medications listed as having been taken 1) prior to initiation of study drug administration and continuing for any period of time following the first administration of study drug or 2) at any time following the first administration of study drug. Prior medications are defined as those medications listed as having been taken prior to initiation of study drug administration, but not taken after initiation of study drug administration.

Both ocular and non-ocular concomitant medications will be summarized using the Safety population. Medications will be tabulated for each treatment group using frequencies and percentages. Subjects may have more than 1 medication per ATC 4 classification. At each level of subject summarization, a subject will be counted once if he/she reports 1 or more medications. Percentages will be based on the number of subjects in each treatment group.

Listings of prior and concomitant medications will be generated separately for ocular and non-ocular data.

Protocol RGN-NK-301/15-110-0006, SAP Version 1.0

13. Dosing Compliance and Treatment Exposure

13.1 Dosing Compliance

[REDACTED]

[REDACTED]

[REDACTED]

[REDACTED]

[REDACTED]

[REDACTED]

[REDACTED]

[REDACTED]

[REDACTED]

[REDACTED]

[REDACTED]

[REDACTED]

[REDACTED]

[REDACTED]

[REDACTED]

[REDACTED]

[REDACTED]

13.2 Treatment Exposure

Treatment exposure will be measured at the subject level; [REDACTED]

[REDACTED]

[REDACTED]

[REDACTED]

[REDACTED]

[REDACTED]

[REDACTED]

[REDACTED]

[REDACTED]

[REDACTED]

[REDACTED]

[REDACTED]

[REDACTED]

[REDACTED]

[REDACTED]

[REDACTED]

[REDACTED]

14. Efficacy Analyses

14.1 Primary Analysis

The primary analysis variables will be presented in subject listings by visit and time point.

[Redacted text block]

[Redacted text block]

14.2 Sensitivity Analyses

[Redacted text block]

[Redacted text block]

[Redacted text block]

[Redacted text block]

[Redacted text block]

Protocol RGN-NK-301/15-110-0006, SAP Version 1.0

- | [REDACTED]
- | [REDACTED]
- | [REDACTED]
- | [REDACTED]
- | [REDACTED]

[REDACTED]

[REDACTED]

[REDACTED]

[REDACTED]

[REDACTED]

[REDACTED]

14.3 Secondary Analyses

The continuous and ordinal secondary efficacy variables collected at each visit will be summarized descriptively [REDACTED]

[REDACTED]

14.3.1 Percentage of Subjects with Complete Healing

The percentage of subjects achieving complete healing of the epithelial defect at Visits [REDACTED]

[REDACTED]

14.3.2 Epithelial Defect Measurement

The epithelial defect will be measured [REDACTED]

[figure not shown]
[REDACTED]

Protocol RGN-NK-301/15-110-0006, SAP Version 1.0

[Redacted]

14.3.3 Epithelial Defect Classification

[Redacted]

[Redacted]

14.3.4 Tear Film Break-Up Time

[Redacted]

Protocol RGN-NK-301/15-110-0006, SAP Version 1.0

[REDACTED]

14.3.6 Visual Acuity (ETDRS)

[REDACTED]

15. Exploratory Analyses

There are no exploratory analyses in this study.

16. Safety Analyses

All safety analyses will be conducted using the Safety Population.

16.1 Adverse Events

An adverse event (AE) is defined as any untoward medical occurrence associated with the use of an investigational medicinal product (IMP) in humans, whether or not considered IMP-related. An AE can

Protocol RGN-NK-301/15-110-0006, SAP Version 1.0

be any unfavorable and unintended sign (e.g., an abnormal laboratory finding), symptom, or disease temporally associated with the use of an investigational product, without any judgment about causality. An AE can arise from any use of the investigational product (e.g. off-label use, use in combination with another drug or medical device) and from any route of administration, formulation, or dose, including an overdose. All AEs will be coded using the Medical Dictionary for Regulatory Activities (MedDRA) Version 22.0.

Documentation regarding the AE should be made as to the nature, date of onset, end date, severity, relationship to study drug, action(s) taken, seriousness, and outcome of any sign or symptom observed by the physician or reported by the subject upon indirect questioning.

Treatment-emergent AEs (TEAEs) are defined as any event that occurs or worsens on or after the day that randomized study treatment is initiated. As treatment is initiated at Visit 1 in this study, all AEs will be considered TEAEs.

Serious adverse events (SAE) are defined as any event that results in death, is life-threatening, requires inpatient hospitalization or prolongation of existing hospitalization, results in persistent or significant disability/incapability, is a congenital anomaly/birth defect, or is medically significant.

An overall summary will be presented that includes the number of AEs and the number and percentage of subjects who experienced at least one AE, by treatment group. This summary will also include breakdowns of AEs further categorized as ocular (study eye, treated fellow eye, and untreated fellow eye separately) or non-ocular, SAEs, AEs by maximum severity, AEs by maximum relationship, and AEs leading to subject withdrawal.

Additional summaries of AEs will be provided showing the number and percentage of subjects who experienced at least one AE. These summaries will be presented by SOC and PT. Non-ocular AEs will be summarized using discrete summary statistics and presented by treatment group at the subject and event level by SOC and PT. Ocular AEs will be similarly summarized at the subject level for all eyes and treated eyes separately. If a subject reports the same PT multiple times within the same SOC, that PT will only be reported once within that SOC. As with the PT, if a subject reports multiple conditions within the same SOC, that SOC will only be reported once. In the summary, SOC will be listed in ascending alphabetical order; PTs will be listed in order of descending frequency for all subjects within each SOC.

Severity of an AE is defined as a qualitative assessment of the degree of intensity of an AE as determined by the Investigator or reported to him/her by the patient/subject. The assessment of severity is made irrespective of relationship to investigational product or seriousness of the event and should be evaluated according to the following scale:

Protocol RGN-NK-301/15-110-0006, SAP Version 1.0

- Mild: Event is noticeable to the subject, but is easily tolerated and does not interfere with the subject's daily activities.
- Moderate: Event is bothersome, possibly requiring additional therapy, and may interfere with the subject's daily activities.
- Severe: Event is intolerable, necessitates additional therapy or alteration of therapy, and interferes with the subject's daily activities.

Summaries of AEs by maximal severity will be presented for ocular AEs and non-ocular AEs separately. The number of subjects with any AEs (along with percentages) will be tabulated by SOC and PT within each SOC by treatment group. To count the number of subjects with any AEs, if a subject has multiple AEs coded to the same PT within the same SOC, the subject will be counted once under the maximal severity.

The relationship of each AE to the study drug should be determined by the investigator using these explanations:

- Definite: When there are good reason and sufficient documentation to demonstrate a direct causal relationship between investigational product and AE;
- Probable: When there are good reasons and sufficient documentation to assume a causal relationship in the sense of plausible, conceivable, likely but not necessarily highly probable.
- Possible: When there is sufficient information to accept the possibility of a causal relationship in the sense of not impossible and not unlikely, although the connection is uncertain or doubtful, for example; due to missing data or insufficient evidence.
- None: When there is sufficient information to accept a lack of a causal relationship, in the sense of impossible and improbable.
- Unclassified: When the causal relationship is not assessable for whatever reason due to insufficient evidence, conflicting data or poor documentation.

Only AEs with a relationship of definite, probable, or possible, or with a missing relationship, will be considered as treatment-related AEs.

The expectedness of an AE should be determined based upon existing safety information about the study drug using these explanations:

- Unexpected: An AE that is not listed in the Investigator's brochure or is not listed at the specificity or severity that has been observed.

Protocol RGN-NK-301/15-110-0006, SAP Version 1.0

- Expected: An AE that is listed in the Investigator’s brochure at the specificity and severity that has been observed.
- Not Applicable: Any AE that is unrelated to the study drug.

AEs that are mentioned in the Investigator's brochure as occurring with a class of drugs or as anticipated from the pharmacological properties of the drug, but are not specifically mentioned as occurring with the particular drug under investigation are to be considered unexpected. AEs that are reported as suspected with respect to relationship to study drug, and are also categorized as unexpected are to be reported directly to Ora, the sponsor, and other authorities as appropriate. Expectedness of the AE will be included in the subject level listings.

As described above, separate summaries will be provided for the following categories of AEs by SOC and PT:

- Ocular AEs in any eye
- Ocular AEs in treated eyes
- Non-ocular AEs
- Treatment-related ocular AEs
- Treatment-related non-ocular AEs
- SAEs

All AEs will be presented in a subject listing. The AEs leading to study treatment discontinuation will be listed separately. In addition, all SAEs will be presented in a separate listing.

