#### 9.1.2 Relationship to Investigational Product

The relationship of each AE to the investigational product should be determined by the investigator using these explanations:

- *Definite*: When there are good reason and sufficient documentation to demonstrate a direct causal relationship between investigational product and AE;
- *Probable*: When there are good reasons and sufficient documentation to assume a causal relationship in the sense of plausible, conceivable, likely but not necessarily highly probable.
- *Possible*: When there is sufficient information to accept the possibility of a causal relationship in the sense of not impossible and not unlikely, although the connection is uncertain or doubtful, for example; due to missing data or insufficient evidence.
- *None*: When there is sufficient information to accept a lack of a causal relationship, in the sense of impossible and improbable.
- *Unclassified*: When the causal relationship is not assessable for whatever reason due to insufficient evidence, conflicting data or poor documentation.

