### 9.10.6 Adverse Events

Adverse events will be coded using the MedDRA dictionary. Frequencies and percentages of subjects with treatment-emergent adverse events (TEAEs), serious TEAEs, and TEAEs causing premature discontinuation will be provided by treatment group. An AE is treatment emergent if it occurs or worsens after the first dose of study treatment. Furthermore, frequencies will be given of subjects with TEAEs by

- System organ class and preferred term,
- System organ class, preferred term and maximal severity,
- System organ class and preferred term for related TEAEs (at least possibly related or unknown relationship), and
- System organ class, preferred term and maximal severity for related TEAEs.

Separate summaries will be provided for ocular (study eye and any treated eye) and non-ocular TEAEs.

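### SAP 16.1 counts a blank causality rating as treatment-related but leaves a recorded not-assessable rating (Unclassified) out of the treatment-related AE tables

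*SAP*

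**What the plan says.** SAP 16.1 and Protocol 9.1.2 use the same five causality ratings: Definite, Probable, Possible, None and Unclassified. Three of the SAP definitions matter here.

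- None: "None: When there is sufficient information to accept a lack of a causal relationship, in the sense of impossible and improbable".
- Unclassified: "Unclassified: When the causal relationship is not assessable for whatever reason due to insufficient evidence, conflicting data or poor documentation".
- Possible takes in cases where a link is accepted as possible, "although the connection is uncertain or doubtful, for example; due to missing data or insufficient evidence".

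After the definitions, SAP 16.1 sets the rule for the related-AE tables: "Only AEs with a relationship of definite, probable, or possible, or with a missing relationship, will be considered as treatment-related AEs". The rule feeds two summaries by SOC and PT, one of treatment-related ocular AEs and one of treatment-related non-ocular AEs.

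Protocol 9.10.6 describes the corresponding table as "System organ class and preferred term for related TEAEs (at least possibly related or unknown relationship". No rating on the protocol's scale is called unknown, and neither document defines the word. SAP section 1 says that SAP methods override those of the protocol. SAP section 18 declares no departures from the protocol's analyses.

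**The concern.** A blank rating and an Unclassified rating both leave causality undetermined, yet the rule sends them in opposite directions. The blank is resolved conservatively, as related. The recorded not-assessable rating is left out, along with the one rating that says a causal link has been rejected. A reader of a treatment-related table would reasonably take the events missing from it to be those judged not related to the drug. Under this rule some of them could be events whose causality nobody could judge.

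There may also be an undeclared change from the protocol. If *unknown relationship* covers Unclassified, the SAP has a narrower definition of a related AE than the protocol, and section 18 does not say so. Because the SAP takes precedence, the narrower rule is the one that would be programmed.

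**Working it through.** No figure in the plan needs reproducing. The check is to pass each possible value of the causality field through both rules and then to bound what one event can do.

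**1. Mapping.** Protocol 9.10.6 is shown under the two narrowest readings of *unknown*.

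| Recorded value | SAP 16.1 | Protocol, unknown = not assessable | Protocol, unknown = blank only |
|---|---|---|---|
| Definite, Probable, Possible | related | related | related |
| Blank | related | not addressed | related |
| Unclassified | **not counted** | **related** | not counted |
| None | not counted | not counted | not counted |

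The SAP column follows from the word *Only*. Unclassified is a recorded rating, so it is not missing, and it is not on the list. The two documents agree only if unknown means a blank field and nothing else. If unknown covers Unclassified, alone or together with blanks, the SAP leaves out events that the protocol counts.

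**2. Do the definitions support excluding Unclassified?** None needs enough information to reject a link. Unclassified, which the protocol defines in the same words ("When the causal relationship is not assessable for whatever reason due to insufficient evidence, conflicting data or poor documentation"), means that such information is lacking. Insufficient evidence is also named as a ground under both Possible, which is counted, and Unclassified, which is not. For an event that fits both descriptions, the investigator's choice of label decides whether it reaches the table.

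**3. Size.** Inputs:

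- 18 subjects enrolled (SAP 4.3).
- Two arms: "It consists of two treatment arms" (SAP 4.1).
- The safety population is randomized subjects with at least one dose (SAP 8.3). I assume this is all 18.
- The allocation ratio is redacted, so none is assumed. The documents give no rate of Unclassified ratings.

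The number of subjects in a related-AE table changes only if someone with an Unclassified AE has no other related AE in that table. One such subject, as a percentage:

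- Overall: 100/18 = 5.6 points.
- Smaller arm: n1 + n2 = 18 means that one arm has at most 9 subjects, so at least 100/9 = 11.1 points.
- Larger arm: between 9 and 17 subjects, so from 100/17 = 5.9 to 100/9 = 11.1 points.

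Non-ocular tables also count events: "Non-ocular AEs will be summarized using discrete summary statistics and presented by treatment group at the subject and event level by SOC and PT". There, each Unclassified event omitted lowers the related-event count by one, whatever else the subject reported.

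**The case against.** The best case for the SAP has five parts.

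- **Blank and Unclassified differ in kind.** A blank is an assessment that was never made, and counting it as related is a cautious imputation. Unclassified is a completed rating. Possible already absorbs many doubtful events, so Unclassified is a residual group. This stands as a reason to expect few such events. It does not explain why not knowing should count as related in one case and not in the other.
- **The SAP may simply implement the protocol.** The two rules have the same shape, and *missing* sits where the protocol has *unknown*. On that reading there is no deviation. The documents do not settle this, so the protocol part of the point is probable rather than proven. The inconsistency within SAP 16.1 remains on either reading.
- **Leaving an event out does not label it unrelated.** That is true of the wording: None and Unclassified remain separate ratings. In the treatment-related tables, however, the two cannot be told apart.
- **The information is not lost.** The events remain in the all-AE summaries and the subject listing, and the overall summary breaks AEs down by maximum relationship. This is a real safeguard and limits the harm. But Unclassified is given no rank in that breakdown, and the treatment-related tables are unchanged by it.
- **SAP 9.2, on missing or inconclusive data, is redacted** and might say something relevant. It cannot be checked. A different rule there would conflict with the explicit sentence in 16.1 and would need reconciling with it.

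It is also fair to say that the size is conditional. No Unclassified AE is known to exist, and the extreme arm splits in the bounds are arithmetic limits rather than expectations.

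**Conclusion.** The concern holds, as a minor one. It is certain from the text that SAP 16.1 counts blank ratings as related and excludes Unclassified. It is likely, but not settled, that this narrows Protocol 9.10.6 without a declared deviation, because that depends on what *unknown relationship* was meant to cover.

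The effect is zero if no AE is rated Unclassified. Subject counts are also unchanged if every subject with such an AE already has another related AE in the same table. Otherwise, given 18 dosed subjects, each affected subject moves the related-AE percentage by the amounts worked out above, which are large per subject only because the trial is small. The rule does not by design favour either arm, and efficacy is untouched.

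**What to change.** Before unmasking, amend the sentence in SAP 16.1 so that the related category consists of Definite, Probable, Possible, Unclassified and missing, leaving None as the only rating outside it. In the same edit, state where Unclassified ranks in the maximum-relationship summary.

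This rule takes in every event that Protocol 9.10.6 counts, whichever way *unknown* is read. If the sponsor confirms that unknown meant blank only, the amended rule is wider than the protocol by the Unclassified events, and section 18 should say so in one line.

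If the present rule is deliberate, keep it, but define *unknown relationship* and, if that definition covers Unclassified, declare the difference in section 18.

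The cost is one added rating in the definition and one derivation flag, with no new data. The drawback is that some not-assessable events that have nothing to do with the drug will be counted as related, which is the same cautious choice the SAP already makes for blanks.
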